5.4.2.2. SAFETY ASSESSMENT

Adverse events

At each visit, adverse events that occur during the visit and that occurred during home use since the previous visit will be documented. Adverse events including those associated with the insertion site will be documented on the appropriate eCRF. Study staff will contact subjects approximately 14 and 45 days post insertion to enable documentation of any adverse events. Subjects will also be reminded to notify clinic staff of any adverse events that occur during the Sensor wear period.

Subjects will be asked to provide information on the following:

- any hospitalizations that may have occurred due to hypoglycemic or hyperglycemic events, and
- any changes in systemic immune function (such as any local or systemic infections and any problems with wound healing independent of Sensor insertion sites).

Insertion Site Assessment

Assessments of the Sensor insertion and removal sites will take place by the clinician at each placement with physical exam and documentation of adverse events. Details can be found in Section 6.

5.4.2.3. LABORATORY TESTING / BIOMETRICS

Every 6 months (See section 5.3), subjects will have blood samples taken for the following laboratory tests:

HbA1c

Every 6 months (See section 5.3), subjects will have the following biometrics collected:

Senseonics, Inc.
Protocol #: CTP-0034, Version 10

Weight

5.4.2.4. **SENSOR REPLACEMENT**

Insertion of New Sensor

A trained study clinician will insert the new Sensor as described in the Visit 1 section above. Each replacement Sensor will be inserted in the alternate arm.

Removal of Old Sensor

A trained study clinician will remove the old Sensor using appropriate technique described in the Eversense CGM Sensor Insertion and Removal Instructions.

Subjects will be advised that they may take over the counter pain medication if needed for any discomfort after the insertion/removal process. No medication, including medication-containing creams and patches is to be applied over the Sensor insertion/removal sites. Subjects will be advised to keep the areas dry for 24-48 hours. Subjects will be advised to change the dressing approximately 48 hours post insertion, and they will check that the healing process is going as expected (minor redness, no swellings, no increased temperature, no increased pain and no sign of infection). The subjects will be instructed to leave the steri-strips in place until they fall off on their own. If the edges of the strips peel back, they may be trimmed. After 48 hours subjects will be advised to change the dressing as required until the incision is healed. Cleaning can be done with normal saline in the clinic, but at home they can use tap water.

QUESTIONNAIRES 5.4.2.5.

Subjects will be asked to fill out the DDS and CGM satisfaction questionnaires at Visit 3 (Day 180) and 5 (Day 365). HCPs will be asked to fill out a short questionnaire regarding their experience periodically.

5.4.2.6. **DATA COLLECTION**

The HCP performing the Sensor insertion/removal will record information about the insertion/removal procedure on the CRF as appropriate.

5.4.2.7. **ESTIMATED VISIT DURATION**

The total duration of the Follow-up/Sensor replacement visit is approximately 2 hours.

Page 27 of 43

5.4.3. VISIT 5/9, DAY 720 FOLLOW-UP/SENSOR REMOVAL FOR SUBJECTS WHO ONLY

Confidential Information Senseonics, Inc. Protocol #: CTP-0034, Version 10 Effective Date:#: 20 March

RECEIVE A 90-DAY OR 180-DAY SENSOR²

The following procedures/instructions will be followed for Follow-up/Sensor removal visit:

5.4.3.1. SENSOR REMOVAL

A trained study clinician will remove the Sensor from the subcutaneous tissue as described above in the Follow-up/Sensor Replacement Visit description.

5.4.3.2. LABORATORY TESTING / BIOMETRICS

Subjects will have blood samples taken for the following laboratory tests:

HbA1c

Subjects will have the following biometrics collected:

Weight

5.4.3.3. DATA COLLECTION

The HCP performing the Sensor removal will be asked to record information about the removal procedure on a CRF as appropriate.

5.4.3.4. QUESTIONNAIRES

Subjects will be asked to fill out the DDS and CGM satisfaction questionnaires at this visit.

5.4.3.5. ESTIMATED VISIT DURATION

The total duration of the Follow-up/Sensor removal visit is approximately 2 hours.

6. ADVERSE EVENTS

The following are definitions and requirements for adverse event monitoring and reporting. The definitions and requirements of local regulations will be followed if different from below.

Senseonics, Inc.

Confidential Information

Page 28 of 43

Protocol #: CTP-0034, Version 10

Effective Date:#: 20 March

² Subjects who transition to 180-day Sensor at 90-, 270-, 450- or 630-day visit, will have a safety evaluation performed at 720-day Visit including examination of Sensor sites and collection of adverse events along with laboratory assessment and questionnaire administration. Follow-up Assessment calls will be made 15 and 45 days after the 720-day visit Ninety (90) days or to Sensor end-of-life (whichever is earlier) following the 720-day visit the subject will return to the clinic for Sensor removal, followed by a phone call for AE assessment. This call designates final participation in the study.

Subjects will contact the Investigator with any questions or concerns. The Investigator will contact Senseonics with questions regarding recording and reporting of adverse events.

6.1. ADVERSE EVENT DEFINITIONS

Adverse Event (AE) is defined as any untoward medical occurrence, unintended disease or injury, or untoward clinical signs (including abnormal laboratory findings) in subjects, users or other persons, whether or not related to the medical device.

- NOTE 1: This definition includes events related to the medical device or the comparator.
- NOTE 2: This definition includes events related to the procedures involved.

NOTE 3: For users or other persons, this definition is restricted to events related to medical devices.

Serious Adverse Event (SAE) is defined as an adverse event that:

- Leads to death;
- Leads to a serious deterioration in the health of the Subject that either:
 - o Results in life-threatening illness or injury; or
 - o Results in a permanent impairment of a body structure or a body function; or
 - o Requires inpatient or prolonged hospitalization; or
 - Results in medical or surgical intervention to prevent life-threatening illness or injury or permanent impairment to a body structure or a body function.
- Led to fetal distress, fetal death or congenital abnormality or birth defect

NOTE: Planned hospitalization for a pre-existing condition, or a procedure required by the CIP, without serious deterioration in health, is not considered a serious adverse event.

Anticipated adverse events are AEs that have been identified as possible adverse events related to the device or procedure.

Unanticipated adverse device effects (UADEs) are defined as any serious adverse effect on health or safety or any life-threatening problem or death caused by, or associated with, a device, if that effect, problem, or death was not previously identified in nature, severity, or degree of incidence in the study plan or application (including a supplementary plan or application), or any

Protocol #: CTP-0034, Version 10

Confidential Information

Page 29 of 43 Effective Date:#: 20 March

f: CTP-0034, version 10

2023

Senseonics, Inc.

other unanticipated serious problem associated with a device that relates to the rights, safety, or welfare of study subjects.

Severity

Mild: Awareness of a sign or symptom that does not interfere with the Subject's usual activity or is transient, resolves without treatment and with no sequelae

Moderate: Interferes with the Subject's usual activity and/or requires symptomatic treatment

Severe: Symptom(s) causing severe discomfort and significant impact on the Subject's usual activities and/or requires treatment

Causality: The causal relationship should be determined with respect to the device, the insertion or removal procedure, or other study-related procedures.

None: The event is not associated with the device or procedure. There is no relation between the event and the device or procedure.

Possibly Related: The temporal sequence between the device or procedure and the event is such that the relationship is not unlikely or there is no contradicting evidence that can reasonably explain the Subject's condition. There is a possibility of any relation between the event and the device or procedure.

Related: The temporal sequence is relevant, or the event abates upon device application completion/removal, or the event cannot be reasonably explained by the patient's condition or comorbidities. The event is related or most likely associated with the device or procedure.

Unknown: There is no evidence or relevant data available to assess the relationship between the event and the device or procedure.

6.2. MONITORING OF ADVERSE EVENTS

Adverse events (AEs) may be volunteered by Subjects, elicited by Investigator or others, or observed. All AEs will be assessed by the Investigator who will determine whether or not the event is related to the device, and/or insertion or removal procedure or other study-related procedure. The Investigator will determine whether or not the event meets the serious criteria. If it is determined that an AE has occurred, the Investigator should obtain all the information required to complete the reporting process, including source documentation. Study staff will contact subjects approximately 14 and 45 days post insertion to enable documentation of any adverse events. Subjects will also be reminded to notify clinic staff of any adverse events that

Senseonics, Inc.
Protocol #: CTP-0034, Version 10

Confidential Information

Page 30 of 43 Effective Date:#: 20 March

occur during the Sensor wear period.

6.2.1. DATA SAFETY MONITORING BOARD

An independent data safety monitoring board will be established prior to the initiation of the study. Members will represent areas of expertise such as internal medicine and endocrinology and biostatistics. The DSMB will develop a charter and hold formal review meetings over the course of the study to assess the ongoing safety information collected as required by their charter. The DSMB will assess if the overall safety profile continues to be appropriate throughout the conduct of the study and immediately reassess if serious events such as death, serious deterioration of health or fetal distress are deemed related to the device.

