3.2. PRIMARY SAFETY ENDPOINT

The primary safety endpoint is the incidence of the composite of infection, secondary procedures to remove the Sensor, or procedure-related adverse events of at least moderate severity.

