3.4. OTHER SAFETY ENDPOINTS

Other safety endpoints include:

- Rate of all device-related and insertion and removal procedure-related adverse events (serious and non-serious events) up to 27 months post-first Sensor insertion
- Rate of device breakage up to 27 months post-first Sensor insertion
- Rate of device-related and insertion and removal procedure-related serious adverse events up to 27 months post-first Sensor insertion
- Subgroup analysis of safety endpoints based on:
 - Age (<65 years vs. >65 years, minimum 40 subjects)
 - Diabetes type (I vs. II)
- Race (non-Caucasian vs. Caucasian)

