6.2.2. CLINICAL EVENTS COMMITTEE

An independent Clinical Events Committee (CEC) will be established prior to the initiation of the study. The CEC will develop and follow a charter which dictates holding frequent meetings as needed whereby individual adverse events are reviewed and adjudicated. All or serious adverse events (whether judged by the site investigators to be related to the device and/or insertion or removal procedure or not) will be assessed for relatedness and severity by the CEC as requested by FDA.

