6.3. ADVERSE EVENT REPORTING

All adverse events (AEs) will be reported by the Investigator and reviewed by the Sponsor in compliance with applicable regulations. Site will follow local IRB reporting requirements for reporting to IRB.

All SAEs must be reported to Sponsor as soon as possible but in no event later than 48 hours after learning of the event. Include Study ID, Study Site, Adverse Event, causal relationship to device and procedure (insertion/removal/other study procedure), seriousness, expectedness, and provide source documentation as soon as available. The AE form of the CRF must be completed within 3 working days of awareness for all SAEs.

All adverse events classified as possibly related or related to the device or procedure will be reported to Senseonics as soon as possible but no later than 3 days of learning of events.

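### The DSMB's one stated trigger for immediate reassessment names the device but not the insertion or removal procedure, although the protocol attributes causality to the two separately

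*Protocol*

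**What the plan says.** Protocol section 6.2.1 gives the DSMB two tasks. The first is to "hold formal review meetings over the course of the study to assess the ongoing safety information collected as required by their charter", judging whether the overall safety profile remains acceptable. The second is event-driven: to "immediately reassess if serious events such as death, serious deterioration of health or fetal distress are deemed related to the device".

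The surrounding sections treat device and procedure as separate causes. Section 6.1 states: "The causal relationship should be determined with respect to the device, the insertion or removal procedure, or other study-related procedures". Under section 6.2 the investigator decides whether an event is "related to the device, and/or insertion or removal procedure or other study-related procedure". Under section 6.2.2 the CEC assesses serious events "whether judged by the site investigators to be related to the device and/or insertion or removal procedure or not". Under section 6.3 each report of a serious event to the sponsor must give "causal relationship to device and procedure (insertion/removal/other study procedure), seriousness, expectedness".

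The endpoints keep the same distinction. Section 3.4 lists "Rate of device-related and insertion and removal procedure-related serious adverse events up to 27 months post-first Sensor insertion". The primary safety endpoint in section 3.2 is the "composite of infection, secondary procedures to remove the Sensor, or procedure-related adverse events of at least moderate severity".

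**The concern.** The relatedness condition in section 6.2.1 is narrower than the causality scheme around it. The phrase *such as* in that sentence extends the list of serious events. It does not extend the list of causes, which contains only the device.

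This matters because procedural harm is a stated subject of the study. Two of the three components of the primary composite are procedural: secondary removal procedures, and procedure-related events of at least moderate severity. Section 3.10 adds the rate of serious adverse events by operator experience with insertion and removal, and section 8.3 expects about 30% of procedures to be done by nurse practitioners and physician assistants. Section 6.4 anticipates excessive bleeding, nerve damage, reactions to local anesthetic, and difficult removals that may need surgery. Any of these, if serious, could be attributed to the procedure and not to the device. At stake is how promptly the independent board would be required to look at such an event.

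**Working it through.** There is no figure in the plan to reproduce, so the check is a comparison of texts.

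**Step 1: which causes each section recognises.**

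| Protocol section | Device | Insertion or removal procedure |
|---|---|---|
| 6.1 Causality | yes | yes |
| 6.2 investigator assessment | yes | yes |
| 6.2.2 CEC scope | yes | yes |
| 6.3 report of a serious event to the sponsor | yes | yes |
| 3.4 serious adverse event endpoint | yes | yes |
| 6.2.1 immediate DSMB reassessment | yes | not named |

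Only the last row omits the procedure.

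**Step 2: follow one event through the plan.** Take a serious event that the investigator attributes to the removal procedure, with no relation to the device.

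- Section 6.3: it reaches the sponsor within 48 hours, with procedure causality stated. The recipient is the sponsor; the section does not mention the DSMB.
- Section 6.2.2: the CEC, which meets as needed, may adjudicate relatedness and severity. The review is qualified as being at FDA's request, and no sentence passes the result to the DSMB.
- Section 6.2.1, first task: the event enters the DSMB's periodic review under the charter.
- Section 6.2.1, second task: the condition is relatedness to the device. It is not met.
- SAP section 5.8: the event is tabulated by relatedness. SAP section 5.10 and protocol section 9.6: it enters interim reports, every 6 months for two years and then yearly. Neither document connects these to a DSMB action.

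**Step 3: look for another trigger.** None of the sections above, nor section 9.3 on early termination, gives an event-driven DSMB reassessment for procedure-related events. The omission in 6.2.1 is therefore not made good elsewhere in the protocol or SAP.

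**The case against.** The strongest reply is that these events are well covered already. The CEC reviews individual events and its scope expressly includes procedural ones, the sponsor hears of serious events within 48 hours, and the DSMB watches overall safety throughout. Section 6.2.1 does not say that the device trigger is exclusive, so nothing prevents the DSMB from convening for a procedural event. Its working rules sit in a charter that is not among the documents. All of this stands, and it limits the point to the stated duty to reassess immediately.

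A second reply is that device and procedure are not so sharply divided. The grade definitions in section 6.1 speak of the device or procedure together, section 1.1 lists the blunt dissector and insertion tool as accessories to the system, and an infection or nerve injury might be attributed to both. This stands in part: some serious procedural events would also be classed as device-related and would meet the trigger. It does not dispose of events attributed to the procedure alone, which section 6.1 and the section 6.3 report allow for.

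A reader might also draw three stronger conclusions that the documents do not support:

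- That section 6.2.1 contains the only event-driven safety review of any kind. The CEC also reviews individual events as needed.
- That a procedural event must wait for the next scheduled DSMB meeting. No meeting schedule is given.
- That the exposure measures the gap. With one insertion and one removal per cycle, 1400 cycles make 2 × 1400 = 2800 procedures, or 2800/273 = 10.3 per inserted subject. That counts procedures, not serious events that miss the trigger. At the planning rate of 2.3%, about 0.023 × 1400 = 32 cycles would have any composite event. The procedure component starts at moderate severity, while serious has its own stricter definition in section 6.1. The number that escapes the trigger could be zero or very small.

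**Conclusion.** The point holds as a gap in the protocol text. Section 6.2.1 requires immediate DSMB reassessment for serious events related to the device and states no such duty for serious events attributed only to insertion or removal. In a study whose primary composite is largely procedural, that trigger is too narrow.

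Its size is modest. Periodic DSMB review, CEC adjudication and sponsor reporting remain in place, and no estimate, test or sample-size figure is affected. How many events would miss the trigger cannot be calculated from the documents.

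The conclusion rests on two conditions: that *device* in section 6.2.1 carries the same meaning as in sections 6.1 to 6.3, where the procedure is listed beside it; and that the charter, which could not be checked, does not already set a wider trigger. If the charter is wider, the protocol text should still be brought into line with it.

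**What to change.** In section 6.2.1, extend the relatedness condition so that it covers serious events deemed related either to the device or to the insertion or removal procedure. Then check that the DSMB charter says the same. The cost is one phrase in the protocol, possibly one in the charter, and perhaps a few ad hoc DSMB reviews.

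Separately, the sponsor may wish to state whether *related* in this sentence includes the grade *possibly related*, which section 6.1 defines on its own. That would be a useful clarification, but it is not part of the defect.

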6.2.2. CLINICAL EVENTS COMMITTEE

An independent Clinical Events Committee (CEC) will be established prior to the initiation of the study. The CEC will develop and follow a charter which dictates holding frequent meetings as needed whereby individual adverse events are reviewed and adjudicated. All or serious adverse events (whether judged by the site investigators to be related to the device and/or insertion or removal procedure or not) will be assessed for relatedness and severity by the CEC as requested by FDA.

6.3. ADVERSE EVENT REPORTING

All adverse events (AEs) will be reported by the Investigator and reviewed by the Sponsor in compliance with applicable regulations. Site will follow local IRB reporting requirements for reporting to IRB.

All SAEs must be reported to Sponsor as soon as possible but in no event later than 48 hours after learning of the event. Include Study ID, Study Site, Adverse Event, causal relationship to device and procedure (insertion/removal/other study procedure), seriousness, expectedness, and provide source documentation as soon as available. The AE form of the CRF must be completed within 3 working days of awareness for all SAEs.

All adverse events classified as possibly related or related to the device or procedure will be reported to Senseonics as soon as possible but no later than 3 days of learning of events.

6.3.1. AE REPORTING PERIOD

Adverse events are reported from enrollment until study participation has ended. Adverse events will be followed until resolution, AE has stabilized, or the study has been completed.

6.3.2. PRE-EXISTING MEDICAL CONDITIONS

Senseonics, Inc.
Protocol #: CTP-0034, Version 10

Confidential Information

Page 31 of 43 Effective Date:#: 20 March

Pre-existing medical conditions or symptoms reported prior to enrollment will not be recorded as an AE. In the event there is a change in the pre-existing medical condition or symptoms due to the device or study-related procedure, then an AE must be recorded.

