6.6. ESCALATION PLAN FOR SUSPECTED STEROID EXPOSURE

Patients will also be checked for complications that could possibly be related to systemic steroid exposure including;

- Poor wound healing
- Increased systemic infections
- Decreased bone density and risk of osteoporosis and/or fractures
- Suppression of the normal hypothalamic/pituitary axis
- Increased insulin resistance

Any subject demonstrating one or more of the conditions that could potentially be a result of steroid exposure listed above will undergo evaluation of the hypothalamic pituitary axis with standard 24-hour urine cortisol test and blood cortisol levels to rule out any systemic suppression as a result of steroid exposure.

6.7. RESIDUAL RISKS ASSOCIATED WITH THE DEVICE/ RMR-0019 US EVERSENSE E3 CGM SYSTEM RISK MANAGEMENT REPORT

Components of the Eversense CGM System are manufactured under the Quality System provisions of ISO 13485:2016 and 21 CFR 820.

Risk analysis has been performed and adequate control put in place as prescribed in relevant provisions of applicable regulatory requirements such as IEC 62304, ISO 14971, and IEC 60601-1, in accordance with the requirements of ISO 13485:2016. Residual risks associated with the device included risks in the categories of electromagnetic and thermal energy, biocompatibility, biologic, chemical and mechanical factors, and user-related error. All identified risks have been reduced as far as possible using various control methods including software revision and revalidation, hardware design modification, packaging and sterilization process validation and labeling revision. The calculated residual risks were determined to be acceptable for conduct of this clinical investigation.

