3.1 Blinding

There is no blinding in this study.

Statistical Analysis Plan		Page 6 of 11
Sponsor	Study	Version
Senseonics	A Post Approval Study to Evaluate the Long-term Safety and Effectiveness of the Eversense® Continuous Glucose Monitoring (CGM) System	1.0

4 Sample Size Determination

At least 273 enrolled subjects will be inserted with Sensors to achieve at least 1400 Sensor cycles. Subjects will be encouraged to remain in the study up to 27 months of follow-up or after at least 1400 Sensor cycles are completed study wide.

Based on data from the PRECISE (n=81 subjects), PRECISE II (n=90 subjects), PRECISION (n=35 subjects) and PMCF (n=1686 subjects) studies, a total of 31 events occurred that would meet the definition of the primary safety endpoint in this study. With a total of 1892 subjects, this equates to an observed rate of approximately 1.6% with an associated 95% confidence interval of 1.1% to 2.3%. As there is variability associated with this sample, as evidenced by the confidence interval, a conservative expected rate of events for this study is 2.3%. The planned sample size of 1400 total cycles) with this expected rate should provide greater than 95% power for the test of the performance goal of 4%.

Meeting the performance goal of 4% for the planned sample size would require a worst-case observation of a rate of approximately 3% or less (i.e., 41 or fewer events among 1400 cycles). This result will be clinically acceptable and similar to results observed in past studies.

5 Statistical Analyses

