5.8 Safety Analyses

Adverse events (AE) will be reported for the ITT primary analysis population. AEs will be tabulated with the number of events and subjects with event for each event type and overall. Rates will be reported as the number of subjects who experience at least one event during the analysis interval out of the total number of subjects with follow-up to the beginning of the analysis interval. Serious adverse events will also be tabulated. The rate of all AEs and SAEs reported in the study will be reported.

All AEs and SAEs will also be summarized by relatedness as described above. Adverse events leading to death or study discontinuation will be provided in listing format.

All device deficiencies will be reported in listing format.

Statistical Analysis Plan		Page 11 of 11
Sponsor	Study	Version
Senseonics	A Post Approval Study to Evaluate the Long-term Safety and Effectiveness of the Eversense® Continuous Glucose Monitoring (CGM) System	1.0

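### Protocol 6.3.2 makes the site's causality judgement a condition for recording worsening of a pre-existing condition, which contradicts the causality-free AE definition in 6.1

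*Protocol*

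**What the plan says.** Protocol 6.3.2 has two sentences. The first sets the default: "Pre-existing medical conditions or symptoms reported prior to enrollment will not be recorded as an AE". The second gives the one stated exception, where there is a "change in the pre-existing medical condition or symptoms due to the device or study-related procedure, then an AE must be recorded". The section is silent on a change from another or an uncertain cause, and it has no clause for serious events.

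The surrounding text works differently:

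- Protocol 6.1 counts as an AE any untoward occurrence "in subjects, users or other persons, whether or not related to the medical device". Causality is a separate grading with four levels: none, possibly related, related and unknown.
- Protocol 6.2 assigns the site-level judgement: "All AEs will be assessed by the Investigator who will determine whether or not the event is related to the device". SAP 3.1 adds: "There is no blinding in this study".
- Protocol 6.2.2 has the CEC assess relatedness and severity "whether judged by the site investigators to be related to the device and/or insertion or removal procedure or not".
- Protocol 6.3 requires all AEs to be reported, SAEs within 48 hours, and possibly related or related events within 3 days.
- Protocol 6.3.3 exempts mild glycemic events but brings back those that meet the serious criteria.
- SAP 5.8 tabulates AEs overall and by relatedness, and states: "The rate of all AEs and SAEs reported in the study will be reported".

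**The concern.** Under 6.1 and 6.2.2 an event is recorded first, the site then grades its cause, and an independent committee can disagree. Under 6.3.2, for anything already present at enrollment, the site decides the cause first, and that decision determines whether there is a record. The site would be settling, without blinding, the question that the CEC was set up to settle.

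This matters in the study population. Every participant has diabetes (Protocol 4.1). The anticipated effects in Protocol 6.4 include hyperglycemia, elevated blood pressure, osteoporosis, glaucoma, impaired wound healing and weight gain, and 6.6 adds "Increased insulin resistance". Any of these can be present before the first Sensor, so an effect of the eluted steroid could show itself as a worsening and not as a new diagnosis. The documents do not say how common such conditions are among participants. If worsening is filtered on the site's view of its cause, the safety tables describe what sites believed to be related plus whatever some sites chose to add.

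**Working it through.** No figure in the plan bears on this point, so the check is textual.

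**Step 1. Apply both rules to the same worsening.**

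| Site's view of cause | Following 6.1 and 6.3 | Following 6.3.2 |
|---|---|---|
| Related | Recorded | Recorded |
| Possibly related | Recorded; sponsor told within 3 days | Unclear: *due to* matches none of the four grades in 6.1 |
| Unknown | Recorded and graded unknown | Not clearly required |
| None | Recorded and graded none | Not required; the default is no record |

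The rules agree only in the first row. The second row also sits badly with 6.3, which expects possibly related events to be reported quickly.

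**Step 2. Trace what happens to an omitted event.** The CEC adjudicates adverse events, the DSMB reviews the safety information that has been collected (6.2.1), and SAP 5.8 tabulates what was reported. All three start from recorded events. Protocol 5.4.2.2 has subjects asked about glycemic hospitalizations, infections and wound healing, but no rule turns an answer into an AE if 6.3.2 has excluded it.

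**Step 3. Identify the results that are exposed.**

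- The AE and SAE tables in SAP 5.8. Rates there count subjects with at least one event. The overall rate loses a subject only if every AE of that subject is omitted; event counts and rows for single event types are more exposed.
- The relatedness summaries in SAP 5.8. The unrelated and unknown categories are thinned directly. The related category loses events that the CEC would have called related but the site did not.
- Comparability across sites. SAP 5.7 examines site differences for the primary endpoints only, so it would not show uneven AE recording.

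**Step 4. Consider the primary composite.** Its components are infection, a secondary removal procedure, and a procedure-related AE of at least moderate severity. Most such events are new and fall outside 6.3.2. Some exposure remains, for instance an infection already present at enrollment that worsens.

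**Step 5. Size.** Let W be the number of worsenings and u the share that a site regards as unrelated or of uncertain cause. A site following 6.1 records W; a site following 6.3.2 strictly records W × (1 − u). With W = 100, an assumed u of 10% gives 100 × 0.9 = 90 records, and an assumed u of 30% gives 100 × 0.7 = 70. The documents give no u, and any value from 0 to 1 is possible. The formula shows the direction and restates the assumption; it does not estimate the loss.

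**The case against.** The strongest reply is that 6.3.2 does not forbid anything. It never uses the word only. Its first sentence can be read as excluding the baseline state, and its second as one sufficient reason to record. An unrelated worsening then falls to 6.1 and 6.3, which require it to be recorded. That reading is possible, but it leaves the causal qualifier with nothing to do. If sites divide between the two readings, recording still differs between them.

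The reply is right to limit the point in several places where a reader might infer more:

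- **Serious worsening is lost.** Not shown. The SAE note in 6.1 excludes planned hospitalization for a pre-existing condition only when there is no serious deterioration, which implies that serious deterioration counts. Section 6.3 asks for causality as a field in the SAE report, not as an entry test. The cover is partial, because an SAE is itself defined as an AE and 6.3.2 lacks the serious-event clause found in 6.3.3.
- **The steroid work-up in 6.6 is filtered.** Not supported. It is triggered by a subject showing a listed condition, with no need for an AE record.
- **The person who did the procedure judges it.** Not supported. The Investigator judges causality, while any trained study HCP may insert or remove Sensors (5.4.1.1).
- **The loss cannot be repaired.** Too strong. Source review and querying of AEs (7.1) allow partial recovery, and HbA1c and weight are collected every 6 months regardless of cause.
- **The device- or procedure-related AE endpoints in 3.4 are badly affected.** Section 6.3.2 requires exactly those events, so they lose only what the site misattributes.

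**Conclusion.** The contradiction stands. On its natural reading, 6.3.2 makes an unblinded site judgement of cause a condition for recording the worsening of a pre-existing condition, against 6.1, 6.2.2 and 6.3. The consequence is possible incompleteness, and differences between sites, in the AE and SAE rates and relatedness summaries of SAP 5.8 and in the events available to the CEC and DSMB.

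The size is unknown. It depends on how many participants have such conditions, how often they worsen, which section each site follows, and how often a site's view of cause differs from the CEC's; the documents give none of these. A reader might infer that the primary safety test against the 4% goal is biased. The documents do not support that beyond a probably small effect, and the point does not bear on the sample size. The plan should be corrected, but this does not put the primary conclusion in doubt.

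**What to change.** Replace the second sentence of Protocol 6.3.2 with wording such as:

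> Any worsening in nature, severity or frequency of a pre-existing condition or symptom after enrollment is recorded as an AE whatever its judged cause. Causality is then graded under 6.1 and adjudicated under 6.2.2.

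Keep the exemption in 6.3.3, repeat the rule in the CRF guidance, and state it in SAP 5.8 so that the tables have a defined basis.

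The cost is one protocol sentence, matching guidance, and somewhat more AE entries at sites. Sample size and analysis methods do not change.

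Timing limits the benefit. Enrollment was to start in the first quarter of 2019 and follow-up to end 60 months later, that is, in the first quarter of 2024. Version 10 is dated 20 March 2023, so on that schedule about one year remained. For follow-up already accrued, use the source review in 7.1 to query unrecorded worsening, and say in the final report which recording rule applied in which period. That adds monitoring effort and will recover only part of what was omitted.
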